Currently, there is only one randomized, controlled trial published in 1999 that compared the use of diuretics alone versus the combination of diuretics and albumin in cirrhotic patients.³ This was a single center conducted in Italy where the investigators used potassium canrenoate and furosemide as diuretics in combination with albumin (25%) 12.5 grams daily. The doses of diuretics used were per center protocol and based on patient clinical response. The results from their study showed that the cumulative rate of response to diuretic treatment of ascites was higher (90.5% vs. 74.7%) (p< 0.05) and length of hospital stay was shorter (p< 0.05) in the group of patients that received diuretics and albumin versus diuretics alone. Although the results were favorable with the use of albumin, the external validity of this study is minimal since it was a single center conducted in Italy in 1999.

III. Study Aims

a. The purpose of this single center, prospective study is to compare the efficacy of two strategies for diuresis in patients with cirrhosis, the use of furosemide (Lasix®) alone versus the combination of furosemide (Lasix ®) and albumin (25%).

IV. Administrative Organization

 a. All research regarding this project will be performed at Rush University Medical Center (RUMC). There will be no inclusion of outside study sites, laboratories, or data management centers.

V. Methods and Materials

- a. Trial Design and sample size
 - i. We will perform a single-center, prospective study with data collected as result of standard of care at RUMC. Patients who are 18 years of age and older, have diagnosed cirrhosis, and present to RUMC with fluid retention will be identified by the Hepatology and/or Surgery attending and be screened for inclusion in the study. Each patient will be randomized into one of the two cohorts and will have 50% chance of being placed into either cohort.
 Cohort 1 will receive furosemide (Lasix) 40 to 80 mg IVP BID for at least 48 hours and cohort 2 will receive combination of furosemide (Lasix) 40 to 80 mg
 - ii. A sample size of 150 patients for this study was estimated based on the previously published study by Gentilini P and colleagues.³ The estimation was based on a success rate of 70% in patients receiving diuretics alone and 90% in patients receiving diuretics plus albumin (alpha = 0.05; beta =0.25).

IVP BID and albumin (25%) 12.5 grams BID for at least 48 hours.

b. Process of Consent

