i. This study is a prospective study so consent from the patient will be obtained prior to enrollment. To obtain consent, the physician will explain the purpose of the study, associated risk and benefits, and answer any additional questions or concerns the patient may ask. If patient decides to enroll in the study, the physician will provide them with the appropriate consent form and all signed forms will be in a securely locked filing cabinet.

c. Participants

i. Adult patients (age ≥18 years old) who have cirrhosis and present to RUMC with fluid retention (ascites, edema, or pulmonary effusions).

d. Inclusion/Exclusion Criteria

 Inclusion criteria: Adult patients (age ≥18 years old), diagnosis of cirrhosis and presents with fluid retention as defined as ascites, edema, or pulmonary effusions requiring diuresis.

ii. *Exclusion criteria*: Patients who are younger than 18 years of age or currently pregnant or who presents with a serum creatinine greater than 2 mg/dL will be excluded.

e. Outcomes

- i. *Primary outcome*: Urine output greater than or equal to 0.5 ml/kg/hour over 24 hours or reduction in weight defined as weight loss of 1 kilogram or greater in a 24-hour period. (While urine output is the best measure for diuretic efficacy, it can often be an unreliable measurement due to patient's not collecting urine properly. Therefore, changes in weight after initiation of diuretic therapy is often used as a surrogate marker for the efficacy of the diuretic therapy, regardless of patient weight at baseline. Several heart failure trials use a change in weight as the endpoint for assessing diuretic efficacy, and this endpoint is also commonly used in clinical practice. Therefore, that is why this endpoint was chosen for this study.)
- ii. **Secondary outcome:** Change in renal function as defined by a chance in serum creatinine from admission to discharge, hospital length of stay, 30-day readmission rates, and patient survival at 6 months and 1 year.

VI. Risk/Benefit Assessment

a. Potential Risks

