This study is a prospective trial however minimal risk to the patient is associated with participation in this study as he/she will be receiving one of two standard of care treatments at our center. Minimal risks associated with the study include experiencing common side effects from the FDA-approved medications used for treatment. The most common side effects of furosemide administered intravenously are low blood pressure, dizziness, headache, or irritation of the skin at the site of injection. In addition, the most common side effects of albumin administered intravenously are high blood pressure, headache, nausea/vomiting or irritation of the skin at the site of injection. There is also a potential risk for invasion of privacy since medical records will be accessed but all data will be de-identified to limit the chance of exposure of PHI.

b. Protection against risks

Physicians will be assessing patients in the study daily and will take precautions against the potential common side effects associated with the FDA-approved medications in this study as stated previously. Precautions include daily monitoring of patients through labs and physical examination and making medical interventions as deemed appropriate.

Data will be collected from the electronic medical record which will be de-identified and maintained in Research Electronic Data Capture (RedCap).

c. Potential benefits to subjects

Patients may benefit from taking part in this study. Based on experience with the use of furosemide (Lasix) and albumin in patients with similar conditions, researchers believe it

may be of benefit to people with cirrhosis. However, because individuals respond differently to therapy, no one can know in advance if it will be helpful for these patients. If the current therapy is not deemed helpful by the physician, the physician will start an alternative standard of care treatment for the patient.

d. Alternatives to participation

Patients may choose to not participate in this study. If participants choose to not participate in this study, the physicians will determine an alternative treatment plan for their fluid retention.

VII. Confidentiality of data and information storage

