a. Data collection will take place on a data collection tool, which will be separate from PHI and will not contain identifiers. RedCAP will be used for data collection and storage. Patient confidentiality will be maintained by recording only de-identified data onto the data collection form. Although the data collected and stored in REDCap will be exported for analysis, the exported data will contain no unique, patient-identifying information. Access will only be available to the research investigators.

Data collected from the electronic medical record at RUMC will include:

- 1. Patient demographics
- 2. Daily lab results including chemistry panel, INR, liver function tests, renal function tests
- 3. Physician's rating of patient's edema (if applicable)
- 4. Dose, frequency, and administration of furosemide (Lasix ®) and/or albumin

VIII. Analysis Plan

a. Statistical analysis will be performed with SPSS statistical package. Patient characteristics will be described using frequencies, means ± standard deviations or medians ± interquartile ranges. Student's t-test will be used to compare continuous variables. Comparisons between groups or categories will be made using chi-squared test. The threshold for statistical significance will be p<0.05.

IX. Literature Cited

- 2. American Association for the Study of Liver Diseases (AASLD): Practice guidelines for the management of adult patients with ascites due to cirrhosis 2012. Hepatology 57(4), 2013.

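### The renal outcome (V.e.ii) has no rule for dialysis or in-hospital death, so an excess of renal failure in one arm would be diluted and could be reversed

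*Combined protocol and SAP*

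**What the plan says.** Section V.e.ii gives one renal measure among the secondary outcomes: "Change in renal function as defined by a chance in serum creatinine from admission to discharge". The word 'chance' is read here as 'change'. The same sentence lists "patient survival at 6 months and 1 year" as a separate outcome.

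Section VIII.a gives the only method that fits a continuous outcome: "Student's t-test will be used to compare continuous variables". Neither section says what value a patient receives after starting dialysis or dying before discharge. The documents never mention dialysis, and they contain no rule for missing values.

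Three other places bear on the point:

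- V.d.ii caps creatinine at entry: a patient "who presents with a serum creatinine greater than 2 mg/dL will be excluded".
- VII.a collects "Daily lab results including chemistry panel, INR, liver function tests, renal function tests", so creatinine before an event should be on file.
- The only treatment item in VII.a is "Dose, frequency, and administration of furosemide (Lasix ®) and/or albumin". Dialysis is not named.

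**The concern.** Discharge minus admission creatinine measures renal change only if nothing but the kidney has moved the creatinine in between. Dialysis breaks that condition, because it clears creatinine directly. A value taken after dialysis has started says little about renal function, yet the definition uses it as though it did.

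In-hospital death raises a different problem. There is no discharge, so a t-test on available values would ordinarily leave the patient out. Both events occur after randomisation and could differ between arms, since the trial tests whether adding albumin changes the response to a diuretic. The patients with the worst renal course are then the ones whose deterioration is understated or absent.

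At stake is the only renal comparison in a trial of intravenous furosemide in cirrhosis. If the handling is left open, it will be chosen after the data are seen, in a study that describes no blinding.

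**Working it through.** The plan states no figure for this outcome, so there is none to reproduce. The total of 150 in V.a.ii was set for the primary outcome. It is used here only to give about 150/2 = 75 per arm under 1:1 allocation.

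**1. When is a dialysed patient scored as improved?** The recorded change is discharge minus admission, and admission is at most 2.0 mg/dL (V.d.ii). The score is negative only if discharge falls below admission. Assumed examples:

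- Admission 1.8, discharge 1.5 on dialysis: 1.5 - 1.8 = -0.3, scored as improved.
- Admission 1.2, discharge 2.5 on dialysis: 2.5 - 1.2 = +1.3, scored as worse.

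Both can happen.

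**2. What can one patient do to an arm mean?** Take an assumed, deliberately unfavourable course: admission 1.5, last value before dialysis 4.0, discharge 1.2. The recorded change is -0.3. The change to the last value before dialysis is +2.5. The gap is 2.8 mg/dL, or 2.8/75 = 0.037 in the arm mean. Two such patients give 0.075 and four (5.3% of the arm) give 0.149. Reaching 0.2 mg/dL, an assumed benchmark, would take 0.2/0.0373 = 5.4 patients, about 7% of the arm.

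**3. What happens to the difference between arms?** Every value in this step is assumed. Patients with neither event change by +0.1. The deterioration is taken as +2.0 for a dialysed patient and +1.5 for one who dies in hospital. Deaths are missing from the recorded data. With dialysis proportion d, death proportion m, and x the change recorded for dialysed patients:

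- Reference mean = (1 - d - m)(0.1) + 2.0d + 1.5m
- Recorded mean = [(1 - d - m)(0.1) + xd] / (1 - m)

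For d = m = 10% the reference mean is 0.08 + 0.20 + 0.15 = 0.430. For 5% it is 0.09 + 0.10 + 0.075 = 0.265. For 2% it is 0.096 + 0.04 + 0.03 = 0.166. As an example of the recorded mean, x = -0.3 gives (0.08 - 0.03)/0.90 = 0.056 at 10% and (0.096 - 0.006)/0.98 = 0.092 at 2%.

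| Events, worse vs better arm | Reference difference | Recorded, x = -0.3 | x = 0 | x = +0.3 | x = +1.0 |
|---|---|---|---|---|---|
| 10% vs 2% | +0.264 | -0.036 | -0.009 | +0.018 | +0.082 |
| 5% vs 2% | +0.099 | -0.013 | -0.003 | +0.006 | +0.029 |
| equal rates | 0 | 0 | 0 | 0 | 0 |

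**4. Where does the sign turn?** For 10% vs 2%, set the recorded means equal: 0.98(0.08 + 0.1x) = 0.90(0.096 + 0.02x). This gives 0.08x = 0.008, so x = +0.1, the change assumed for the patients with neither event. Below that the worse arm looks better. Above it the worse arm still looks worse, but by much less. Even at x = +1.0 the loss is 1 - 0.082/0.264 = 69% in the first row and 1 - 0.029/0.099 = 71% in the second.

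**The case against.** The strongest reply is that this is a modest gap in a secondary outcome and is easy to overstate. Much of that stands.

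- A reader might infer that dialysis is always scored as improvement. It is not: step 1 shows a dialysed patient correctly scored as worse.
- A reader might infer that the plan excludes in-hospital deaths. No section says so. Exclusion is the likely default of a t-test, and the daily laboratory results would permit another choice.
- A reader might infer that these deaths count nowhere. They count in the survival outcome. That does not repair the renal comparison.
- A reader might infer that the arm with more renal failure will look better. Reversal needs dialysed patients to record less change than the others; dilution is the more general effect.
- The patient in step 2 is hand-picked, and the +2.5 is measured to the last value before dialysis, which is not the plan's own endpoint. Four such patients still fall short of the assumed 0.2.
- The list in VII.a is not exhaustive. It also omits weight and urine output, which the primary outcome needs, so the absence of dialysis does not prove that it will go unrecorded.
- Transplant during the stay might seem a third case, but the documents never mention it and it is not part of this point.
- The sentence in VI.c, "If the current therapy is not deemed helpful by the physician, the physician will start an alternative standard of care treatment for the patient", concerns a change of therapy. It says nothing about dialysis or creatinine and supports neither side.

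What the reply does not answer is that the definition, applied exactly as written, uses a creatinine lowered by dialysis as a measure of renal function and has no value for a patient who dies before discharge. That can produce a wrong result, so it is more than a missing detail.

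**Conclusion.** The concern holds in a limited form. As defined in V.e.ii and analysed under VIII.a, the renal comparison would dilute an excess of renal failure or in-hospital death in one arm and could reverse it. Its actual size cannot be computed, because the documents give no rates of dialysis or in-hospital death. Under the assumed values above, roughly 70% or more of the reference difference is lost when the event rates differ, and none is distorted when they are equal. The result rests on deaths being left out by default and on dialysed patients recording no more than +1.0 mg/dL. The documents do not support the stronger statement that the worst renal outcomes are necessarily counted as good or ignored. This is a cheap improvement to a secondary outcome.

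**What to change.** In V.e.ii, state that creatinine measured after the start of dialysis is not used. State also that the last value before dialysis or in-hospital death, whichever comes first, replaces the discharge value. The daily laboratory results in VII.a already supply it.

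In VIII.a, report the number of patients with dialysis and with in-hospital death, by arm, beside the mean creatinine change. Add the dates of dialysis start and in-hospital death to VII.a.

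A worst-rank comparison of all randomised patients may be added as a sensitivity analysis, with the order of dialysis and death fixed beforehand. It should not be the main analysis: it turns a renal measure into a composite with death, counts deaths again that already enter the survival outcome, and is not in mg/dL.

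The cost is a few sentences and two chart items. The last earlier value may understate the final deterioration, and it gives no credit to a patient whose kidneys recover after temporary dialysis. That is why the counts belong alongside the mean. Treatment, the primary outcome and the sample size do not change.

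### Hospital length of stay has no start point, enrolment window or rule for in-hospital death, so a t-test on the raw stay could include pre-randomisation days and count an early death as a short stay

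*Combined protocol and SAP*

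**What the plan says.** Section V.e.ii lists, after the change in creatinine, "hospital length of stay, 30-day readmission rates, and patient survival at 6 months and 1 year". Length of stay is not defined further: there is no start, no end and no rule for a patient who dies in hospital. The creatinine item in the same sentence does have a time frame, "serum creatinine from admission to discharge", but that phrase belongs to creatinine only.

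On enrolment, V.a.i says that patients who "present to RUMC with fluid retention will be identified by the Hepatology and/or Surgery attending and be screened for inclusion in the study". Consent and randomisation follow, and each patient "will have 50% chance of being placed into either cohort". The exclusions in V.d.ii are age under 18, pregnancy, and a patient "who presents with a serum creatinine greater than 2 mg/dL will be excluded". None concerns days already spent in hospital.

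On analysis, VIII.a says "Student's t-test will be used to compare continuous variables". Categorical comparisons use chi-squared. No time-to-event or competing-risk method is given. The list of data items in section VII names neither the randomisation date, the discharge date nor the discharge status.

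**The concern.** Two separate things can go wrong if the outcome is analysed in its ordinary sense, as raw days from admission to discharge compared by t-test.

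- **Before randomisation.** Days in hospital before allocation cannot be affected by the arm. If the delay varies between patients, it adds variance to the outcome and lowers the chance of detecting a real difference.
- **At the end of the stay.** A patient who dies on day 3 and a patient who goes home well on day 3 both contribute 3 days. If one arm has more early deaths, its mean stay falls and it looks better for the wrong reason.

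Section II reports a shorter stay as one of two benefits seen with albumin in the earlier randomised trial, so readers are likely to look for this result here. Death is foreseen, since survival is a secondary outcome in the same sentence. If the definition stays open, the start point and the handling of deaths could also be chosen after the results are seen.

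**Working it through.** **What the plan gives.** There is no length-of-stay calculation to reproduce. The one relevant figure is the total: "A sample size of 150 patients for this study was estimated", taken here as 75 per arm. It was set for the primary response rate. The stated inputs (70% vs 90%, alpha 0.05, beta 0.25) give a two-sided total of 110, or 130 with continuity correction, rather than 150. That has no bearing on this point, and 150 is used below only as the number of patients. Every SD, delay and death rate below is an assumption, because the documents give none.

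**1. Noise from pre-randomisation days.** Let s0 be the SD of days before randomisation and s1 the SD of days after it, independent of each other.

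Variance ratio = (s0² + s1²) / s1². Effective patients lost, for this outcome only = 150 × (1 − 1/ratio).

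- s0 = 2, s1 = 5: (4 + 25)/25 = 1.16; 150 × (1 − 1/1.16) ≈ 21.
- s0 = 3, s1 = 5: (9 + 25)/25 = 1.36; 150 × (1 − 1/1.36) ≈ 40.
- Range for s0 from 1 to 3 and s1 from 4 to 6: from 37/36 = 1.03 to 25/16 = 1.56.
- s0 = 0 (all randomised on the day of admission): ratio 1, loss nil.

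The same effect as power, for an assumed true difference of 2 days, 75 per arm and two-sided alpha 0.05: power = Φ(2 / (SD × √(2/75)) − 1.96), with SD = √(s0² + s1²). For s1 = 5 and s0 = 0 this is Φ(2/0.816 − 1.96) = Φ(0.49) = 69%.

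| s1 | s0 = 0 | s0 = 1 | s0 = 2 | s0 = 3 |
|---|---|---|---|---|
| 4 | 87% | 84% | 78% | 69% |
| 5 | 69% | 67% | 62% | 56% |
| 6 | 53% | 52% | 49% | 45% |

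Allocation is 1:1 at random, so the delay has the same expected value in both arms. It costs power but does not shift the comparison.

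**2. Bias from deaths.** Assume a stay with mean 8 and SD 5 days, deaths spread evenly from 0.5 to 5 days (mean 2.75), and no effect of treatment on time to discharge. The apparent shortening in the arm with more deaths is roughly the difference in death rate × (8 − 2.75).

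- 5% vs 10%: 0.05 × 5.25 ≈ 0.26 days.
- 5% vs 15%, or 10% vs 20%: 0.10 × 5.25 ≈ 0.53 days.

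A simulation with 75 per arm, 4,000 trials per row and a t-test on raw stay gives:

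| In-hospital death | Apparent shortening in the higher-mortality arm | That arm significantly shorter |
|---|---|---|
| 5% vs 5% | 0.00 days | 2.5% of trials |
| 5% vs 10% | 0.27 days | 4.8% |
| 5% vs 15% | 0.53 days | 8.8% |
| 10% vs 20% | 0.54 days | 10.0% |

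The nominal figure in the last column is 2.5%. With equal death rates there is no bias. Unlike the noise, this effect remains even if every patient is randomised on the day of admission.

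**The case against.** A reader might infer that the plan itself counts pre-randomisation days and scores a death as an early exit. It states neither. Counting from admission is the ordinary meaning of the term, and the neighbouring creatinine item uses that time frame, but for length of stay it remains an inference. The treatment of deaths is the default result of a missing rule.

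A reader might also infer that late enrolment is expected. The documents do not describe it. Eligibility is worded throughout in terms of patients presenting with fluid retention, which suggests enrolment near arrival. What stands is that no criterion enforces this.

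Nor do the documents support the reading that pre-randomisation days bias the comparison, since randomisation balances them in expectation. The 21 or 40 patients are not lost to the trial: the figures concern the precision of this one outcome and need assumed delay SDs of 2 or 3 days. The bias from deaths needs an imbalance. The examples have two or three times the mortality in one arm, and the separate survival outcomes might reveal a large difference.

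Finally, the protocol does not present length of stay as a measure of time to recovery or as a key outcome. It is one of several unranked secondary outcomes, and the protocol itself regards the earlier trial's external validity as minimal. These objections limit the weight of the point. They do not supply the missing definition, and the only analysis on offer would still treat an early death as a favourable value.

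**Conclusion.** The concern holds as a gap in definition whose default result is a poorer analysis. With no start point, no enrolment window and no death rule, a t-test on stay in its ordinary sense would carry any pre-randomisation days as noise and would favour an arm with more early in-hospital deaths.

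Under the assumptions shown, the noise inflates the variance by 3% to 56%, and by nothing if randomisation falls on the day of admission. The death effect is about 0.3 days at 5% vs 10% and about 0.5 days at 5% vs 15% or 10% vs 20%. In the last two cases the higher-mortality arm is significantly shorter in 9% to 10% of trials instead of 2.5%. It is nil when death rates are equal. The true size cannot be fixed from the documents. The primary outcome and the conclusion drawn from it are unaffected. This is a cheap improvement of minor priority.

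**What to change.** - **V.e.ii:** define the outcome as time from randomisation to discharge alive.
- **VIII.a:** compare it by cumulative incidence of discharge alive, with in-hospital death as a competing event, for example by Gray's test. If every index stay is followed to discharge or death, an equivalent is a log-rank comparison with deaths held at a time beyond the longest stay. Report total stay from admission descriptively.
- **VII, data list:** add days from admission to randomisation, days from randomisation to discharge, and discharge status (alive or dead). Day counts rather than dates keep the collection form de-identified.

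The cost is one sentence in each of V.e.ii and VIII.a and one line in VII, with no extra patients, visits or change to treatment. The downside is slightly less direct comparability with the stay reported in the earlier trial, which the descriptive total stay largely covers. A narrower change, stating only the start point and a death rule, would close the gap in definition. The outcome above is preferred because a death then never counts as an early discharge.

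### 30-day readmission is compared on its own with no rule for deaths, so by default an arm with more early deaths can look better

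*Combined protocol and SAP*

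**What the plan says.** Section V.e.ii lists the secondary outcomes: change in creatinine, length of stay, and then "30-day readmission rates, and patient survival at 6 months and 1 year". Readmission is therefore an outcome in its own right, and death is assessed only at the two later times.

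Section VIII gives the only method that applies to a yes/no outcome: "Comparisons between groups or categories will be made using chi-squared test". It adds: "The threshold for statistical significance will be p<0.05". It does not say whether tests are one- or two-sided.

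Four things are not stated anywhere: who is in the denominator of the readmission rate, when the 30 days start, how a patient who dies is counted, and whether deaths within the window are reported. The list of data to be collected, in section VII, names neither readmission nor vital status.

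**The concern.** Death and readmission compete: a patient who dies in hospital or soon after discharge can no longer be readmitted. If every randomised patient is classed as readmitted or not and the two proportions are compared, such a patient counts as 'not readmitted', which is the good result. A treatment that increased early deaths would then tend to lower its own readmission rate.

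Limiting the comparison to patients discharged alive removes only part of this. Deaths after discharge still count as favourable, and the patients compared are selected by an event that happens after randomisation, so the arms are no longer protected by the randomisation.

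The issue is practical here. The patients are in hospital with complications of cirrhosis, and the plan itself follows survival to one year, so some deaths are expected. At stake is a misleading secondary result, possibly read as a benefit of one strategy on hospital use.

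**Working it through.** The plan gives no readmission or death rate, so on this point it has no figure of its own to reproduce. From the plan I take the total ("A sample size of 150 patients for this study was estimated") and the allocation ("will have 50% chance of being placed into either cohort"), hence about 75 per arm, and the 0.05 threshold, read as two-sided. Every rate below is an assumption.

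**Step 1: all randomised patients in the denominator.** Let r be the readmission risk among patients who do not die early, equal in both arms. Let d be the proportion who die by day 30 without having been readmitted.

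- Readmission rate = (1 − d) × r
- Death or readmission = d + (1 − d) × r

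With r = 0.30:

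| d | Readmission | Death or readmission |
|---|---|---|
| 5% | 0.95 × 0.30 = 28.5% | 5.0 + 28.5 = 33.5% |
| 10% | 0.90 × 0.30 = 27.0% | 10.0 + 27.0 = 37.0% |
| 15% | 0.85 × 0.30 = 25.5% | 15.0 + 25.5 = 40.5% |

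At deaths of 15% versus 5%, the arm with more deaths looks 3.0 points better on readmission and is 7.0 points worse on death or readmission. At 10% versus 5% it looks 1.5 points better and is 3.5 points worse.

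Over a wider range (r from 20% to 40%; deaths of 5% in one arm and 10% to 20% in the other), it looks 1.0 to 6.0 points better on readmission and is 3 to 12 points worse on the composite.

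**Step 2: only patients discharged alive.** Let h be the proportion who die in hospital. The rate becomes (1 − d) × r / (1 − h). With r = 0.30 and deaths of 15% versus 5%:

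- No deaths in hospital: 25.5% versus 28.5%, a gap of 3.0 points.
- One third in hospital (h = 5% versus 1.67%): 25.5/95 = 26.8% versus 28.5/98.33 = 29.0%, a gap of about 2 points.
- All in hospital: 25.5/85 = 30% versus 28.5/95 = 30%, no gap. The 10-point difference in deaths is then simply not visible.

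**Step 3: size against the trial's precision.** At 75 per arm, the standard error of a difference near 27% is √(2 × 0.27 × 0.73 / 75) = 0.0725, or 7.25 points. The 3.0-point distortion is about 0.4 of a standard error and the 1.5-point one about 0.2.

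With no distortion, the chance of a significant readmission result favouring a given arm is 2.5%. For the arm with more deaths it rises to 4.0% at deaths of 10% versus 5% and to 6.1% at 15% versus 5%. Across the wider range it is about 4% to 12%.

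**Step 4: a harsher assumption.** Suppose the patients who die are those who would otherwise have been readmitted, so that death or readmission is equal in both arms, at 30%. With deaths of 15% versus 5%, readmission is 30 − 15 = 15% versus 30 − 5 = 25%, and the chance of a significant result favouring the arm with more deaths is about 33%. This shows how much the size depends on the assumption; the conclusion does not rest on it.

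**The case against.** A reader might infer that the protocol instructs analysts to code deaths as 'not readmitted'. It does not. It is silent, and that coding is only what a plain yes/no comparison of all patients yields by default. An analyst could choose another denominator. This stands: the defect is a missing rule.

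A reader might also infer that the comparison misleads whichever denominator is used. Step 2 does not support that. If all early deaths occur in hospital, and survivors in both arms have the same readmission risk, the discharged-alive rate is 30% versus 30%. Selection by a post-randomisation event is still a concern in principle, but under these assumptions it produces no reversal.

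The rates are invented for illustration, and 15% versus 5% is a threefold imbalance. With balanced deaths the distortion is zero, and at this sample size 1 to 6 points would usually not reach significance. A patient readmitted before dying is counted correctly by a plain rate, so d must be read as deaths without prior readmission; taking all early deaths would exaggerate the effect. All of this stands.

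Deaths are not ignored either, since any death by day 30 also counts in 6-month survival. That helps, but it does not show deaths in the window that the readmission rate covers.

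Finally, a composite answers a different question from readmission. That is a reason to add it beside the readmission rate and not to replace that rate.

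**Conclusion.** The concern holds as a missing rule with a predictable and unfavourable default. As written, the readmission comparison can favour the arm with more early deaths, and no planned outcome reports deaths in that window. Under the illustrative rates the reversal is 3.0 points in favour on readmission against 7.0 points against on death or readmission. This rests on assumed mortality and readmission rates and on a real imbalance in early deaths. If such deaths are few or balanced, the effect is small or absent.

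Nothing in the documents indicates which arm, if either, would have more early deaths. It would also be wrong to infer that the trial's main result is at risk: this is one of several secondary outcomes and the primary conclusion is unaffected. It is a low-priority improvement, worth making because it is cheap if done before the data are seen.

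**What to change.** In V.e.ii and VIII:

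- Keep the 30-day readmission rate, and state its denominator and the day from which the 30 days run.
- Add death or readmission by 30 days after discharge, in all randomised patients, with in-hospital death counted as an event.
- Report readmissions and deaths separately by arm over that same window.
- Also report deaths by 30 days from randomisation. The composite's window is length of stay plus 30 days. Length of stay is itself an outcome, and section II reports that it was shorter with albumin in the cited trial, so the window may differ by arm.
- Add readmission and vital status to the data list in section VII.

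The cost is a few sentences and two data items. Deaths are already needed for the survival outcomes. The data come from the centre's own medical record, so the plan should say how readmissions and deaths elsewhere will be found. The composite is less comparable with published readmission rates, which is why the readmission rate stays beside it.
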